Activity	Wk				Wk 16 20	Wk 24	Wk 36	Wk 48	Monthly	Every 12 Weeks Until Study Completion ^a	Every 24 Weeks Until Study Completion ^a	Every 48 Weeks Until Study Completion ^a	Final/ PD Visit	30-Day F/U Visit/ Call ^b	
	Wk	Wk	Wk	Wk											
In-home urine pregnancy test ^m									X						
Central lab tests	X	X	X	X						X					
hsCRP ⁿ															
Blood chemistry ^o															
Hematology (CBC)															
Urinalysis ^p															
ESR (local lab)	X	X	X	X						X					X
HBV screening ^q			X	X						X					
In vivo pharmacodynamic biomarkers			X	X						X					
Dispense study drug and subject dosing diary	X	X	X	X						X					
Review and retain a copy subject dosing diary and perform drug reconciliation	X	X	X	X						X					X

BL = Baseline Visit; CBC = complete blood count; csDMARD = conventional synthetic disease-modifying anti-rheumatic drug; ECG = electrocardiogram; F/U = Follow-up; HAQ-DI = Health Assessment Questionnaire – Disability Index; hsCRP = high-sensitivity C-reactive protein; NRS = numerical rating scale; PDD = Prenature Discontinuation; PhGA = Physician's Global Disease Activity; PPD = purified protein derivative; PtGA = Patient's Global Assessment of Disease Activity; RCT = randomized controlled trial; SAE = serious adverse event; SJC = Swollen Joint Count; TB = tuberculosis; TJC = Tender Joint Count; VAS = visual analog scale; Wk = Week

- a. Every 12, 24, or 48 weeks from the Week 48 visit.
- b. This visit is 30 days after last close of study drug for those subjects who complete Period 2. A 30-day follow-up phone call should also be performed for subjects who have completed PD visit to determine the status of any ongoing AEs/SAEs or the occurrence of any new AEs/SAEs.

Table 3. Studies Activities (Period 2) (Continued)

- c. At Week 24 (after Week 24 assessments have been performed), if a subject fails to meet LDA criterion (LDA defined as CDAI ≤ 10) investigator should adjust the subject's background RA therapies. Initiation of or change in corticosteroids, NSAIDs, acetaminophen, or adding or increasing doses of csDMARDs (concomitant use of up to 2 csDMARDs except the combination of MTX and leflunomide; see Inclusion Criterion 3) is allowed as per local label.
- d. Prior to other procedures. For morning stiffness, duration will be captured only if NRS rating is > 0 .
- e. TB testing should be performed every 48 weeks after Week 48 and at PD in subjects with previous negative Quantiferon and/or PPD tests. Subjects with new evidence of latent TB should initiate prophylactic treatment immediately per local guidelines. TB Testing/TB prophylaxis for additional details.
- f. Obtain chest x-ray every 48 weeks after Week 48 and PD for subjects with TB risk factors as identified by the TB risk assessment form, or for subjects living in areas endemic for TB, or for subjects with a newly positive Quantiferon-TB Gold test (and/or PPD skin test) after baseline.
- g. ECGs will be performed every 48 weeks after Week 48 and for subjects who prematurely discontinue from the study. An ECG may be performed at any visit if deemed necessary by the Investigator.
- h. Blood pressure, pulse rate, body temperature, and respiratory rate should be performed before blood draws are performed.
- i. A full physical exam is required every 24 weeks after Week 48. A symptom-directed physical exam may be performed when necessary.
- j. Starting at Week 24 and thereafter, subjects who failed to show at least 20% improvement in TJC and SJC compared to baseline at 2 consecutive visits should be discontinued from the study.
- k. CDAI calculation requires input of SJC28 + TJC28 + PtGA + PhGA into IRT system. At Week 24, investigator should optimize background RA therapies in subjects who failed to achieve CDAI ≤ 10 .
- l. For women of childbearing potential, a urine pregnancy test will be performed at all visits and monthly at home between scheduled study visits. Pregnant subjects must discontinue from the study. Study Procedures Pregnancy Test for additional details.
- m. Starting at Week 24, for women of childbearing potential, in-home urine pregnancy tests will be performed monthly. The results of the monthly at home tests will be communicated to the site. If a urine pregnancy test is positive, the subject must stop dosing, come in to the clinic and have blood drawn for a serum pregnancy test that will be analyzed at the central laboratory.
- n. hsCRP results from the central laboratory will remain blinded to Sponsor, Investigator, study site personnel, and the subject. Treatment assignment may be unblinded to Sponsor only when the last subject completes Period 1 (Week 12 visit) for an analysis for regulatory purposes. For safety evaluations of signs and symptoms of infection and management of adverse events, the Investigator may locally test procalcitonin. However, results of tests such as hsCRP, serum amyloid A and procalcitonin may be blunted in subjects taking a JAK inhibitor, thereby limiting the clinical utility of these tests in the setting of a possible safety assessment or adverse event management. It should also be noted that any hsCRP, CRP, serial SAA, or serial procalcitonin local tests reported to the Investigator will be recorded as protocol deviations.
- o. Minimum 8-hour fast. If a subject is not able to fast when necessary, due to unforeseen circumstances, the non-fasting status will be recorded in study source documentation.

Table 3. Studies Activities (Period 2) (Continued)

p. Dipstick urinalysis will be completed by the central lab at all required visits. Specified abnormal macroscopic urinalyses defined as leukocytes, nitrite, protein, ketones, or blood greater than negative, or glucose greater than normal will be followed up with a microscopic analysis at the central laboratory.

q. In HBs Ab positive (+) subjects and/or HBC Ab positive (+) subjects, HBV-DNA PCR test should be performed in every 12 weeks. The investigator has to consult with the medical expert of the sponsor in case where the recurrence of HBV-DNA is observed. This measure is not necessary in case of the patients with the history of HBV vaccine and HBs Ab positive (+).

Note: Visit window is ± 7 days for the study. Any of the procedures may be performed at an unscheduled visit at the discretion of the Investigator.

4.3 Sample Size

Sample size was estimated based on the previous global Phase 2 trial (Study M13-537). Assuming an ACR20 response rate of 46% for placebo group, 62% for low dose group (7.5 mg QD), 68% for middle dose group (15 mg QD) and 80% for high dose group (30 mg QD) of Upadacitinib, the sample size to have 90% power and two-sided alpha of 5% to detect a statistically significant dose-response using Cochran-Armitage test will be 42 subjects per group. And the sample size to demonstrate the superiority of Upadacitinib compared to placebo will be 46 subjects to provide the 90% power and 5% of two-sided alpha. Taking 5% of drop-out rate into consideration, sample size will be 48 per group (total sample size: 192 subjects).

4.4 Interim Analysis

An unblinded analysis will be conducted after all subjects have completed Period 1 (Week 12). Additional unblinded analyses may be conducted for the purpose of regulatory submission. Study sites and subjects will remain blinded for the duration of the study (Periods 1 and 2).

4.5 Data Monitoring Committee (DMC) Activities

An independent external Data Monitoring Committee (DMC) is used to review unblinded safety data at regular intervals during the conduct of the study. The DMC will provide recommendation to an AbbVie Point of Contact on whether to continue, modify, or terminate studies after each review. When needed, high level unblinded efficacy data may also be requested by the DMC and be reviewed so that the DMC can assess benefit: risk of any emerging safety differences.

5.0 Analysis Populations and Analysis Windows

5.1 Analysis Populations

Full Analysis Set (FAS)

The Full Analysis Set (FAS) includes all randomized subjects who received at least one dose of study drug. The FAS will be used for all efficacy and baseline analyses.

Per Protocol Analysis Set

The Per Protocol Analysis Set represents a subset of the FAS and consists of all FAS subjects who did not meet any major protocol deviations during Period 1 of the study. Additional analysis of the primary efficacy endpoint will be conducted on the Per Protocol analysis set, in order to evaluate the impact of major protocol deviations.

Major protocol deviations (ICH deviation and other clinically significant non-ICH deviation) will be identified prior to database lock.

Safety Analysis Set

The Safety Analysis Set consists of all subjects who received at least one dose of study drug. For the Safety Analysis Set, subjects are assigned to a treatment group based on the "as treated" treatment group, regardless of the treatment randomized. The "as treated" is determined by the treatment the subject received during the majority of the subject's drug exposure time in the study.

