Subjects must have been on a stable dose of csDMARD(s) for \geq 4 weeks prior to the first dose of study drug and must remain on a stable dose until Week 24; the csDMARD dose may be decreased only for safety reasons. Subjects who do not achieve CDAI \leq 10 at Week 24 should have background medication(s) adjusted or initiated after assessments for Week 24 have been completed. Starting at Week 24 (after Week 24 assessments have been performed), initiation of or change in corticosteroids, non-steroidal anti-inflammatory drugs (NSAIDs), acetaminophen, or adding or increasing doses in up to 2 csDMARDs (concomitant use of up to 2 csDMARDs except the combination of MTX and leflunomide) is allowed as per local label.

[figure not shown]
Subjects with prior exposure to at most one bDMARD for RA may be enrolled in the study (up to 20% of total study population) after the required washout period is satisfied and if they have limited exposure (< 3 months), OR response to bDMARD but had to discontinue that bDMARD due to intolerance (regardless of treatment duration). These subjects will be equally stratified across all treatment groups. Subjects who are considered bDMARD inadequate responders, as determined by the Investigator, are not eligible.

Subjects who complete the Week 12 visit (end of Period 1) will enter the blinded long-term extension portion of the study, Period 2 (until regulatory approval of RA indication in Japan). Subjects who are assigned to Upadacitinib treatment groups in Period 1 will continue to receive Upadacitinib 7.5 mg QD, 15 mg QD or 30 mg QD per original randomization assignment in a blinded manner. Subjects who are assigned to placebo in Period 1 will be switched to receive Upadacitinib 7.5 mg QD, 15 mg QD or 30 mg QD per their pre-specified randomization assignments at Week 12 in a blinded manner per pre-specified randomization assignments.

An unblinded analysis will be conducted after all subjects have completed Period 1 (Week 12). Additional unblinded analyses may be conducted for the purpose of regulatory submission. Study sites and subjects will remain blinded for the duration of the study (Periods 1 and 2).

[figure not shown]
Study design schematics of Period 1 and Period 2 are shown in [Figure 1](#) and [Figure 2](#) respectively.

Figure 1. Period 1 Study Design

csDMARD = conventional synthetic disease modifying anti-rheumatic drug; QD = once daily; RA = rheumatoid arthritis

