7.0 Patient Disposition

The following will be summarized by randomized treatment group as well as overall:

- number of subjects randomized,
- number of subjects included in key analysis populations (Full Analysis Set and Per Protocol Analysis Set for primary efficacy analysis, Safety Analysis Set for Period 1),
- number of subjects who completed Period 1,
- number of subjects who entered Period 2,
- number of subjects on-going in Period 2 (if applicable),
- number of subjects who completed overall study (Period 1 and Period 2) (if applicable).

This summary will be repeated by site.

Prematurely discontinued study drug details will be further summarized separately for Period 1 and Period 2 as follows.

Period 1

The number and percentage of subjects completed Period 1 and prematurely discontinued study drug in Period 1 will be summarized by randomized treatment group, with the primary reasons for discontinuation collected from CRF by the following categories:

- Adverse event (AE)
- Withdrew consent
- Lost to follow-up
- Lack of efficacy
- Other.

Subjects may have more than one reason for discontinuing, but only the primary reason will be summarized.

In addition, the number and percentage of subjects enrolled in Period 2 will also be summarized by randomized treatment group.

Period 2

Period 2 patient dispositions and reason for discontinuation of study drug will be summarized for overall and by actual treatment in Period 2 defined as follows:

1. Upadacitinib (ABT-494) 7.5 mg QD
2. Upadacitinib (ABT-494) 15 mg QD
3. Upadacitinib (ABT-494) 30 mg QD

Among the subjects who entered Period 2, the number and percentage of subjects completed, on-going (if applicable), and prematurely discontinued in Period 2 will be summarized.

For subjects who prematurely discontinued study drug the primary reasons for discontinuation will be summarized by the following categories (as collected in CRF):

- Adverse event (AE)
- Withdrew consent
- Lost to follow-up
- Lack of efficacy
- Other.

Subjects may have more than one reason for discontinuing, but only the primary reason will be summarized.

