10.0 Safety Analysis

10.1 General Considerations

Safety analyses will be carried out using the Safety Analysis Set. There are two sets of planned safety analysis: safety analysis for Period 1, and long-term safety analysis.

Safety Analysis for Period 1

Standard safety analysis by the "as treated" treatment groups of Upadacitinib 7.5 mg QD, Upadacitinib 15 mg QD, Upadacitinib 30 mg QD, and combined placebo groups will be performed on safety data in Period 1. No protocol-defined treatment switching will occur prior to the end of Period 1.

The standard safety analyses will include reporting of adverse events (AEs), laboratory, and vital signs measurements. Frequency tables of subjects with treatment-emergent adverse events (TEAEs) by system organ class (SOC) and by preferred term (PT) as in the Medical Dictionary for Regulatory Activities (MedDRA) dictionary will be provided by treatment group. Mean changes from baseline in all continuous laboratory parameters and vital signs variables at each visit will be summarized by "as treated" treatment group. Frequency tables of subjects meeting criteria for potentially clinically significant vital sign values and for potentially clinically significant laboratory values will be provided by treatment group. Missing safety data will not be imputed.

Long Term Safety Analysis

Long term safety analyses that account for protocol-defined treatment switching include reporting of AE rate adjusted by cumulative exposure, mean change from baseline in

laboratory parameters and vital sign variables, and rate of potentially clinically significant laboratory and vital signs values. The treatment-emergent adverse event (TEAE) rate per 100 patient-years of exposure will be presented by actual treatment received at the time of AE (as described in Section 10.2.2.2). Listing of subjects with TEAEs by SOC and PT will be provided. Mean changes from baseline in all continuous laboratory parameters and vital signs variables at each visit will be summarized by "as treated" treatment group sequences defined as follows (as described in Section 10.3.3 and Section 10.4.3). Frequency tables and listings of subjects meeting criteria for potentially clinically significant vital sign values and for potentially clinically significant laboratory values will be provided by actual treatment received at the time of event. Missing safety data will not be imputed.

"As treated" treatment group sequences:

1. Upadacitinib (ABT-494) 7.5 mg QD

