2. Upadacitinib (ABT-494) 15 mg QD
3. Upadacitinib (ABT-494) 30 mg QD
4. Placebo → Upadacitinib (ABT-494) 7.5 mg QD
5. Placebo → Upadacitinib (ABT-494) 15 mg QD
6. Placebo → Upadacitinib (ABT-494) 30 mg QD

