10.2.2.1 Adverse Events Overview

The number and percentage of subjects experiencing TEAEs will be summarized by "as treated" treatment group and overall for the following AE categories.

- All TEAEs
- Treatment-emergent serious adverse events (SAEs)
- Treatment-emergent severe adverse events
- TEAEs reasonably possibly related to study drug
- TEAEs of special interest
- TEAEs leading to discontinuation of study drug
- TEAE leading to death

Additional AEs may be considered for tabulation/summary based on recommendations from Clinical and Safety as deemed appropriate.

For TEAEs of special interest, the point estimate and 95% CI (using normal approximation) will be provided for the treatment difference in AE percentage between each Upadacitinib dose group and the combined placebo group.

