10.3 Analysis of Laboratory Data

10.3.1 Variables and Units

All laboratory parameters to be collected in this study are listed below. Laboratory parameters will be reported using the standard international (SI) units.

Table 14. List of Laboratory Variables

Laboratory Variables
Hematology
White Blood Cell (WBC) Count
Red Blood Cell (RBC) Count
Hemoglobin
Hematocrit
Platelets count
Neutrophils
Basophils
Eosinophils
Lymphocytes
Monocytes
Bands

Table 14. List of Laboratory Variables (Continued)

Laboratory Variables

Chemistry

Total Bilirubin
Alkaline Phosphatase (ALP)
Serum glutamic oxaloacetic transaminase (SGOT/AST)
Serum glutamic pyruvic transaminase (SGPT/ALT)
Total Protein
Albumin
Glucose
Triglycerides
Blood Urea Nitrogen (BUN)
Creatinine
Uric acid
Sodium
Potassium
Calcium
Inorganic Phosphorus
Creatine Phosphokinase (CPK)
Chloride
Bicarbonate
Cholesterol
LDL cholesterol
HDL cholesterol
International Normalized Ratio (INR) reflux only

Urinalysis

Specific Gravity
pH
Protein
Glucose
Ketones
Blood
Microscopic Examination (if needed)
Urobilinogen

Table 14. List of Laboratory Variables (Continued)

Laboratory Variables
Urinalysis (continued)
Bilirubin
Leukocytes
Nitrites
Other
hs-CRP
QuantiFERON-TB Gold
IgG and IgM
ESR

10.3.2 Analysis of Laboratory Data for Period 1

The laboratory data will be summarized by the "as treated" treatment groups (Upadacitinib 7.5 mg QD, Upadacitinib 15 mg QD, Upadacitinib 30 mg QD, and combined placebo groups) and overall.

10.3.2.1 Assessment of Mean Change from Baseline and Mean Percentage Change from Baseline in Clinical Laboratory Variables

Analyses of mean change from baseline in continuous hematology, chemistry, and urinalysis variables which are measured longitudinally will be performed by visits and by "as treated" treatment group. For each change from baseline analysis, the following summary statistics will be presented for each treatment group: sample size, baseline mean, visit mean, and the mean, standard deviation, and median of the changes from baseline. An ANOVA model with treatment as a factor will be used to test statistical significance for the change from baseline mean among different treatment groups.

In addition, similar analyses will be conducted for mean percentage change from baseline in hemoglobin, NK cells, LDL, HDL and triglycerides.

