10.3.2.4 Assessment of Liver Elevations

According to FDA's Guidance for Industry Drug-Induced Liver Injury: Premarketing clinical evaluation (July 2009), when aminotransferase (AT) abnormalities indicating hepatocellular injury are accompanied by evidence of impaired hepatic function (bilirubin elevation $> 2 \times$ ULN), in the absence of evidence of biliary obstruction (i.e., significant elevation of ALP) or some other explanation of the injury (e.g., viral hepatitis, alcohol hepatitis), the combined finding (i.e., Hy's Law cases) represents a signal of a potential for the drug to cause severe DILI.

For the purpose of assessing for potential Hy's law cases, the frequencies and percentages of subjects with post baseline liver specific function test values that meet the following criteria of potential clinical interest will be summarized by "as treated" treatment group:

- ALT $\geq 3 \times$ ULN
- ALT $\geq 5 \times$ ULN
- ALT $\geq 10 \times$ ULN
- ALT $\geq 20 \times$ ULN
- AST $\geq 3 \times$ ULN
- AST $\geq 5 \times$ ULN
- AST $\geq 10 \times$ ULN
- AST $\geq 20 \times$ ULN
- TBL $\geq 2 \times$ ULN
- Alkaline phosphatase $\geq 1.5 \times$ ULN
- ALT and/or AST $\geq 3 \times$ ULN and concurrent TBL $\geq 1.5 \times$ ULN
- ALT and/or AST $\geq 3 \times$ ULN and concurrent TBL $\geq 2 \times$ ULN

10.3.3 Analysis of Long Term Laboratory Data**10.3.3.1 Assessment of Mean Change from Baseline and Mean Percentage Change from Baseline in Clinical Laboratory Variables**

Analyses of mean change from baseline in continuous hematology, chemistry, and urinalysis variables which are measured longitudinally will be performed by visits and by "as treated" treatment group sequences as described in Section 10.1. For each change from baseline analysis, the following summary statistics will be presented for each treatment group: sample size, baseline mean, visit mean, and the mean, standard deviation, and median of the changes from baseline.

In addition, similar analyses will be conducted for mean percentage change from baseline in hemoglobin, NK cells, LDL, HDL and triglycerides.

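### SAP 5.1 defines 'as treated' by majority of exposure over the whole study, which cannot give the Period 1 placebo group or the placebo-to-upadacitinib sequences in SAP 10.1

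*SAP*

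**What the plan says.** - **SAP 5.1, Safety Analysis Set.** Subjects are grouped by 'as treated', not by randomisation, and the label "is determined by the treatment the subject received during the majority of the subject's drug exposure time in the study". No period is named. The Per Protocol set in the same section is limited to Period 1.
- **SAP 4.2.** There are three placebo groups of 16. "Subjects who are assigned to placebo in Period 1 will be switched to receive Upadacitinib" at one of the three doses, at Week 12.
- **SAP 10.1, Period 1 safety.** Tables are by 'as treated' group: three upadacitinib doses and combined placebo. The section adds: "No protocol-defined treatment switching will occur prior to the end of Period 1".
- **SAP 10.1, long-term safety.** Six sequences carry the same 'as treated' label. Three start on placebo, for example "Placebo → Upadacitinib (ABT-494) 7.5 mg QD". SAP 10.3.3.1 (laboratory) and 10.4.3 (vital signs) summarise mean changes by "treatment group sequences as described in Section 10.1".
- **SAP 7.0.** The disposition summary counts a "Safety Analysis Set for Period 1", but no section defines a period-specific label for it.
- **Protocol 8.1.1.3.** Groups follow the treatment actually received. The majority rule appears only in the SAP.

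**The concern.** One rule has to serve two uses, and as worded it serves neither once a placebo subject has been on upadacitinib longer than on placebo. The label would then be upadacitinib, so that subject's Week 0 to 12 events, laboratory values and vital signs would be counted under a drug not yet taken. The rule also returns a single treatment, so it cannot produce a two-treatment sequence.

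Period 1 is the only randomised, placebo-controlled safety comparison in the study. The outputs that depend on the label include:

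- the interval estimate for events of special interest, given for "the treatment difference in AE percentage between each Upadacitinib dose group and the combined placebo group" (SAP 10.2.2.1);
- the other Period 1 adverse event tables (10.2.2.2 to 10.2.2.6);
- the laboratory ANOVA, shift tables, Fisher tests and liver elevations (10.3.2.1 to 10.3.2.4);
- the vital-sign tables (10.4.2);
- the long-term laboratory and vital-sign mean changes by sequence (10.3.3.1, 10.4.3).

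The move would pull differences against placebo towards zero. An empty placebo column would be noticed. A partial move at an intermediate data cut would be much harder to see.

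**Working it through.** **1. Planned group sizes (SAP 4.2, 4.3).** With 192 subjects allocated 3:3:3:1:1:1 (12 parts), each dose group has 192 × 3/12 = 48 and each placebo group 192 × 1/12 = 16. Combined placebo is 3 × 16 = 48. This agrees with the plan.

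**2. When the label changes.** Inputs from SAP 4.2: the Week 12 visit is Day 85 with a 3-day window, and the last Period 1 dose is taken the day before it. Assume uninterrupted daily dosing, with Period 2 dosing starting on the visit day. For a Week 12 visit on Day w:

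- placebo days = w − 1;
- upadacitinib days by Day t = t − w + 1;
- upadacitinib first exceeds placebo on Day t = 2w − 1.

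For w = 85 there are 84 placebo days and the label changes on Day 169. For w = 82 it changes on Day 163, and for w = 88 on Day 175. In the nominal case the two exposures are equal on Day 168, and the rule does not resolve that tie.

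**3. Whether this can arise by the first unblinded analysis.** That analysis follows completion of Week 12 by all subjects (SAP 4.4). When the last subject is at Day 85, anyone first dosed at least 84 days earlier is at Day 85 + 84 = 169 or later. Enrolment spread over about 12 weeks is therefore enough, if exposure is counted to that cut. The documents do not give the enrolment length. SAP 4.4 allows later unblinded analyses, and Protocol 5.6.4 expects about three and a half years of dosing.

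**4. Effect on the columns.** Let k placebo subjects move, split equally, so m = k/3 join each dose. With event rates d on drug and p on placebo, and moved subjects having the placebo rate, the expected difference is

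(48d + mp)/(48 + m) − p = [48/(48 + m)] × (d − p).

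The factor does not depend on d or p.

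| Moved k | Placebo 48 − k | Each dose 48 + k/3 | On placebo throughout Period 1 | Factor |
|---|---|---|---|---|
| 0 | 48 | 48 | 0% | 1.00 |
| 12 | 36 | 52 | 4/52 = 7.7% | 48/52 = 0.92 |
| 24 | 24 | 56 | 8/56 = 14.3% | 48/56 = 0.86 |
| 36 | 12 | 60 | 12/60 = 20% | 48/60 = 0.80 |
| 48 | 0 | 64 | 16/64 = 25% | not computable |

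**5. Late data cut with drop-out.** Suppose the planned 5% (SAP 4.3) all leave before the switch point. Then 48 × 0.95 = 45.6 move and 2.4 stay. Each dose column becomes 48 + 15.2 = 63.2, of which 15.2/63.2 = 24% were on placebo throughout Period 1. Over an assumed drop-out range of 0% to 20%, 48 to 38 move, 0 to 10 stay, and columns are 64 to 61 (25% to 21% placebo).

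**6. Sequences.** SAP 10.1 lists them without saying how a subject is assigned, so 5.1 is their only rule too. A single-treatment label cannot give the three placebo-first sequences. This does not depend on the data cut or on enrolment.

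**7. Outputs not affected.** Primary efficacy uses randomised groups (SAP 9.2.1). Exposure is summarised by dose received (8.0). Long-term adverse event rates, potentially significant laboratory and vital-sign values, and liver elevations use the treatment at the time of the event (10.2.3, 10.3.3.2, 10.3.3.3, second part of 10.4.3).

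**The case against.** The strongest reply is that 'treatment' in SAP 5.1 means the assigned regimen. SAP 4.2 lists each placebo-to-dose path as a treatment group, and combined placebo in Period 1 is simply Groups 4 to 6 pooled, as Protocol 8.1.4.1 does for efficacy. A placebo-to-7.5 mg subject then keeps one regimen throughout, and the majority rule only handles dispensing errors. That would make Section 10 work, but it does not fit a rule written in terms of the treatment received over most of the exposure time.

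A second reply is that other text already settles the groups. SAP 10.1 names them and notes that no planned switch precedes the end of Period 1. SAP 5.2 caps the Week 12 safety window at the first Period 2 dose. Protocol 8.1.5.1 asks for Period 1 alone, by treatment actually received. This stands as evidence of intent. It does not replace the one derivation rule that a programmer or validator would code from.

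A third reply is that harm needs a literal-minded programmer, and that the number moved runs from 0 to 48. This also stands: the table shows scenarios, not an estimate, and a complete move would be caught.

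Finally, a period-by-period rule leaves rare cases open, such as ties or mis-dosing that gives a sequence not among the six. The current rule does not resolve those either.

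**Conclusion.** The concern holds. SAP 5.1 is wrong as written: it states a rule that, followed literally, gives the wrong Period 1 groups after about Day 169 and never gives the placebo-first sequences. The surrounding text shows that a Period 1 label was intended, so this is a defect of definition. It should be fixed, but it does not show that the safety analysis will be wrong.

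The sequence conflict is certain from the wording. The size of the Period 1 effect is conditional on literal programming with exposure counted to the data cut, uninterrupted daily dosing, an equal split over doses, and moved subjects having the same event rate as other placebo subjects. Under those assumptions expected differences shrink by 8%, 14% or 20% when 12, 24 or 36 subjects move. At a late cut almost no placebo subjects remain. At the first unblinded analysis the effect could be nil.

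**What to change.** Replace the last sentence of the Safety Analysis Set definition in SAP 5.1 with wording such as:

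> For Period 1 safety analyses, 'as treated' is the treatment taken for most of the subject's drug exposure in Period 1. For long-term analyses by sequence (Section 10.1), the sequence combines the Period 1 label with the treatment taken for most of the drug exposure in Period 2; a subject with no Period 2 dosing takes the randomised Period 2 treatment. Where Sections 10.2.3, 10.3.3 and 10.4.3 specify it, the treatment at the time of the event is used.

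With subjects dosed as assigned, combined placebo and each dose group stay at 48 and each placebo-first sequence at 16, whatever the data cut. A tie rule, and a line on sequences outside the six listed, could be added at the same time, but the correction does not depend on them.

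The cost is one sentence and an updated derivation that gives a Period 1 label and a sequence. No new data are needed, and Section 10 and the sample size do not change.
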